16.5 Data/specimen handling for multi-site research

N/A - This study is not multi-site.

study staff.

16.6 Data sharing

We may share coded data (e.g., questionnaire, behavioral task, location) with researchers within or outside of UW-Madison to address future research questions not included in this application,

with a complementary study being conducted at the Center for Healthy Minds (i.e., the "BeWell Study"; PI: [name]; Protocol: 2021-0991) which is utilizing many of the same survey and behavioral task measures, and/or with journals where open data sharing policies are encouraged or are a requirement for publication (e.g., PLoS ONE). Coded data may be shared as Supplemental Information uploaded to journal websites and/or shared on a UW data sharing website such as "Minds@UW" (http://researchdata.wisc.edu/data-access-2/) or UW-Madison Box (https://uwmadison.box.com). UW-Madison Box will only be used to transfer coded data and will not be used for long-term data storage. Data will be directly uploaded to the journal website or the data sharing website. Confidentiality will be protected by coding the data with new subject numbers. The code linking the new subject numbers to the original subject numbers will be kept on our secure server and will be maintained by study staff.

We may share fully de-identified data from the study on data sharing platforms (e.g., OpenNeuro, NIMH Data Archive) for use by non-collaborators. Data shared on data sharing platforms will be uploaded via the internet. Confidentiality will be protected by stripping the data of all identifiers, including HIPAA identifiers.

We may follow-up with participants from this study in future research studies. We will ask participants on the consent form if they would like to be contacted about future studies. If they agree, their contact information (e.g., name, phone number, email address, home address) will be kept on the Center for Healthy Minds' secure server indefinitely. Only authorized study staff will have access to this information. The participant's contact information will not be stored with their data. Future studies may include analysis of the information from this study alone or in combination with data collected in other studies. Any future research utilizing these data will be submitted as a separate application to the IRB prior to their use, if required by IRB policies and/or guidance.

17.0 Provisions to Protect the Privacy Interests of Participants

17.1 Steps to protect privacy interests

- Procedures will be performed in a private area where others cannot see the procedures being performed or overhear the conversation between subjects and researchers.
- ☑ All members of the study team are up to date on their institutional HIPAA training.
- ☐ The study is not collecting information that could pose legal or reputational risks to participants.

All study procedures will be completed remotely in a setting of the participant's choice. We will recommend that participants complete remote study procedures in a private room.

17.2 Justification for sensitive information

The study screener will ask questions about current and/or past symptoms of various mental illnesses. The study surveys include questions related to negative childhood experiences, depression, anxiety, and stress. One aim of the study is to investigate whether the meditation training intervention reduces perceived stress, which is related to depression and anxiety. Current

or past history of various psychiatric disorders may confound aims of the study and thus are part of the exclusionary criteria.

17.3 Steps to make participants feel at ease

The study description, consent form, and introduction to the surveys/interview will all include language stating that 1) participation is voluntary, 2) some questions may be of a sensitive nature, and 3) participants may skip any items that they are not comfortable answering, except for certain required items (e.g., the PSS is required because it is a primary study measure). We will provide participants with a description of the procedures that will be performed during study visits and will ask participants if they are comfortable proceeding. We will let participants know that they can ask questions or tell us concerns at any time and we would be happy to help.

18.0 Sharing of Results

18.1 Whether results will be shared with participants or others

All measures (surveys, behavioral task, & location) are for research purposes only and individual results may not be meaningful. We will not share individual results with participants or report results in participant health records.

18.2 Plans to share study results with the public

We will share study results with the public via manuscripts and/or open source databases. The Center for Healthy Minds website and/or other social media platforms may share information about study results and/or publications.

19.0 Data and Specimen Banking

19.1 Description of data and specimen banking

We may bank any data collected during this study (e.g., questionnaire, behavioral task, location) for future use to address research questions not included in this protocol. Banking of data will not be optional. Banked data will be stored indefinitely on ICTR's instance of REDCap and on a password-protected secure server with access limited to authorized study staff.

19.2 Information associated with banked data and specimens

Study data will be coded with the participant ID. The code linking data to identifying information will be kept on a password-protected secure server and ICTR's instance of REDCap with access limited to authorized study staff.

19.3 Procedures to release banked data and specimens

There are no limits on future use of banked data. Any future research utilizing these data will be submitted as a separate application to the IRB prior to their use, if required by IRB policies and/or guidance. Other researchers inside and outside of UW-Madison may request banked data from the Principal Investigator.

19.4 Withdrawing banked data or specimens

Participants may withdraw their banked data from future research use. If we receive a withdrawal request from a participant, we will destroy all of their banked data.

20.0 Study Analysis

20.1 Statistical hypotheses

H1: HMP vs. waitlist participants will show (a) lower scores on the perceived stress scale, (b) improved performance on the pattern separation task, and (c) increased "experiential diversity" measured using GPS location tracking.

H2: Within the HMP group, greater decreases in perceived stress will be correlated with improvements/increases in outcomes b-c.

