1.0 Study Summary

Study Title	Brain and Meditation (BAM) Study			
Brief Summary	This study is a randomized controlled trial to test the impact of an			
•	app-based meditation program on perceived stress and behavioral and			
	brain correlates of stress. Healthy adult participants between the ages			
	of 25-65 will be enrolled in the study for about 4-5 months.			
Number of study sites	1			
Study Design	Participants will be randomized into one of two groups: the			
	intervention group or the waitlist control group. The intervention			
	group will use a mobile health app for four weeks. Participants will			
	complete pre-intervention, weekly, post-intervention, and 3-month			
	follow-up surveys and tasks.			
Primary Objective	Test for hypothesized group differences in perceived stress and			
	hippocampal-dependent behavior following participation in a 4-week			
	meditation program.			
Secondary	Within the meditation group, determine whether reductions in			
Objective(s)	perceived stress are associated with changes in hippocampal-			
	dependent behavior.			
Research	Healthy Minds Program (HMP) – a mobile health meditation training			
Intervention(s)/	program			
Investigational				
Agent(s)				
Drugs/devices used	Healthy Minds Program (HMP) – a mobile health meditation training			
on study (including	program			
any IND/IDE #)				
Study Population	25-65 year old healthy adults with no significant experience with			
	meditation			
Sample Size	150 participants			
Study Duration for	4-5 months			
individual				
participants				
Study Specific	mHealth = mobile health			
Abbreviations/	HMP = Healthy Minds Program			
Definitions				

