2.3 Scientific background for, rationale for, and significance of the research

Meditation training dramatically reduces perceived stress and has benefits for psychiatric conditions associated with elevated perceptions of stress, such as depression and post-traumatic stress disorder (PTSD). Access to in-person programs, however, is limited due to associated cost and lack of available services.

Research on behavioral and neurobiological mechanisms contributing to individual differences in perceived stress is largely limited to correlational, cross-sectional studies. The inclusion of behavioral outcomes in research on a meditation training program will allow us to draw causal inferences regarding mechanisms of perceived stress.

Prior research has demonstrated that greater roaming entropy, or more diverse activity around one's lived environment, is associated with greater psychological well-being in humans (Heller et al., 2020) and with greater neurogenesis in the hippocampus of laboratory mice. We are interested in examining whether a meditation intervention that seeks to improve well-being will do so in part through effects on greater roaming entropy, and whether individual differences in roaming entropy (either at baseline, or in response to the meditation intervention) are associated with behavioral changes consistent with greater hippocampal neurogenesis.

In this project, we will conduct a randomized controlled trial of the HMP vs. waitlist control to test the efficacy of a fully remote, 4-week meditation intervention on reducing perceived stress in a healthy adult population. Using behavioral measures with a known neurobiological basis (pattern separation and real-world exploratory behavior), we will investigate hypothesized mechanisms associated with individual differences in perceived stress and how they may be impacted by meditation training.

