3.0 Study Objectives and Endpoints

3.1 Specific aims

- To assess efficacy of a 4-week mHealth meditation training program on reducing perceived stress.
- To investigate the effects of meditation training on candidate behavioral and brain mechanisms of perceived stress: behavioral pattern separation and real-world experiential diversity.
- To assess the extent to which lower levels of perceived stress following mindfulness training is associated with corresponding changes to these candidate mechanisms.

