3.2 Hypotheses

- Intervention participants will show larger reductions in perceived stress relative to waitlist control participants at post-intervention and follow-up timepoints.
- Intervention participants will show improved pattern separation behavior relative to waitlist control participants at post-intervention and follow-up timepoints.
- Intervention participants will show increased real-world "experiential diversity" assessed using GPS location tracking relative to waitlist control participants at post-intervention and follow-up timepoints.
- Changes in hippocampal-dependent behavior will be correlated with reductions in perceived stress.

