3.3 Primary and secondary study endpoints

Primary endpoints

• Scores on the perceived stress scale at post-intervention (T5) controlling for baseline (T1)

Secondary endpoints

- Performance on the behavioral pattern separation task (post-intervention and follow-up/T6)
- PROMIS depression and anxiety (post-intervention and follow-up)

Tertiary and exploratory endpoints

- Symptoms of PTSD measured using the PCL-5 (post-intervention and follow-up)
- PROMIS sleep disturbances (post-intervention and follow-up)
- Five-facet mindfulness questionnaire, awareness subscale (post-intervention and follow-up)
- NIH toolbox Loneliness (post-intervention and follow-up)
- Healthy Minds Index (post-intervention and follow-up)
- Real-world experiential diversity measured using continuous GPS location tracking (Measured continuously throughout study participation)
- Trajectories of change for self-report outcomes assessed on a weekly basis

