13.0 Procedures Involved

13.1 Study design

This will be a two-group randomized controlled trial assessing the impact of the Healthy Minds Program (HMP), a meditation-based well-being app, on behavioral and self-reported outcomes associated with stress and well-being in 150 individuals. Participants will be adults ages 25 to 65

years who have no significant experience with meditation, have access to a smartphone, and are willing to follow through on all aspects of the protocol. The primary endpoint will be scores on the perceived stress scale. Participants will be randomized to the HMP or waitlist control group at a 2:1 ratio. Prior to randomization, participants will complete initial surveys and a computerized task remotely. Participants assigned to the HMP group will complete a 4-week well-being program remotely using an app on their smartphone. Each week participants will also complete a set of online surveys/tasks. Waitlist control participants will also complete the online surveys/tasks each week for 4 weeks. All participants will complete a final set of follow-up surveys/tasks 3 months later. In addition, we will track participant location using GPS smartphone technology throughout the study.

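### Does H2's correlation within the HMP arm alone need a further rule before the trial can speak about mechanisms of perceived stress?

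*Combined protocol and SAP*

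**What the plan says.** All references are to the combined protocol and SAP.

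- **Section 20.1, H2:** "Within the HMP group, greater decreases in perceived stress will be correlated with improvements/increases in outcomes b-c". Outcomes b and c are pattern separation and GPS-measured experiential diversity. H1(a) to (c) compare the randomised arms on perceived stress and on these same two behaviours.
- **Section 1.0, secondary objective:** it opens "Within the meditation group, determine whether reductions in" and goes on to ask about an association with changes in hippocampal-dependent behaviour.
- **Section 3.1, third aim:** the extent to which "lower levels of perceived stress following mindfulness training is associated with corresponding changes to these candidate mechanisms".
- **Section 3.2, last hypothesis:** "Changes in hippocampal-dependent behavior will be correlated with reductions in perceived stress". No arm is named. Section 20.4 describes Pearson correlations of difference scores, also without naming an arm.
- **Section 2.3, background:** including behavioural outcomes in research on a meditation programme "will allow us to draw causal inferences regarding mechanisms of perceived stress". The authors also say they are interested in "whether a meditation intervention that seeks to improve well-being will do so in part through effects on greater roaming entropy".
- **Section 13.1:** "Waitlist control participants will also complete the online surveys/tasks each week for 4 weeks". Waitlist change scores will therefore exist for perceived stress and the task.
- **Section 3.3:** pattern separation is a secondary endpoint; GPS diversity is tertiary or exploratory.

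**The concern.** H2 is the only planned analysis that links two changes, and it uses one arm. Anything unrelated to the app that eases stress and improves memory or mobility in the same people, such as a lighter month at work, produces the correlation H2 looks for. The waitlist arm, which experiences the same background influences, is left out of this relation.

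Section 2.3 speaks of causal inference and of an effect operating through roaming entropy, but the plan describes no mediation analysis. Nor does it say how H1(b) and H1(c) are to be read alongside H2. A significant HMP-only correlation could then be reported as evidence of mechanism even if the app had not changed the behaviour. The unnamed arm in sections 3.2 and 20.4 adds a second worry, that analysts might pool the arms.

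**Working it through.** **Inputs.** Section 20.2 gives 150 participants, 2:1 allocation and 10% dropout: 100 × 0.9 = 90 HMP and 50 × 0.9 = 45 waitlist completers. It gives d = 0.5 for perceived stress at 0.05, and r = 0.41 with 80% power at 0.0125. Assumed here: two-sided tests, equal dropout in both arms, normal change scores, and d = 0.5 and a 0.05 level for the behaviours (the plan states these only for perceived stress).

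**Step 1: the plan's correlation figure.** By Fisher's z, n = ((2.498 + 0.842)/atanh 0.41)² + 3. With atanh 0.41 = 0.4356 this is about 62. At n = 90 the detectable r is tanh(3.339/√87) = 0.343, and power for r = 0.41 is Φ(0.4356 × √87 − 2.498) = 94%. The stated 0.41 is therefore not reproduced for the HMP arm. It errs towards understating power, is a separate matter, and does not affect what follows.

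**Step 2: what H2 alone can distinguish.** Share of simulated trials with a significant HMP-only correlation (10,000 per scenario):

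| True r | Common cause, app does not change the behaviour | Behaviour mediates the effect |
|---|---|---|
| 0.41 | 94.2% | 94.3% |
| 0.3 | 65.2% | 65.0% |
| 0.2 | 27.4% | 28.1% |

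The columns agree by construction, because both scenarios have the same within-arm correlation. These are detection rates for an association that exists, not false-positive rates. They show that H2 is a test of association, which is how sections 1.0, 3.1 and 20.1 present it.

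**Step 3: is the randomised check missing?** No. H1(b) and H1(c) test whether the app changes each behaviour, with the mixed models of section 20.4. Under a common cause with no arm effect on the behaviour, that arm test is significant in about 5% of trials. A reader of the planned results would see a correlation without an arm effect.

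**Step 4: would a formal joint rule add protection?** Take the obvious one: an arm effect on the behaviour at 0.05 plus an arm-adjusted, two-arm association at 0.0125, with r = 0.41.

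| Truth | Rule met |
|---|---|
| Common cause, no app effect on the behaviour | 4.9% (2.5% in the hypothesised direction) |
| Mediation, d = 0.5 on the behaviour | 77.2% |
| App affects both outcomes directly, common cause links them | 77.1% |
| App changes the behaviour but not perceived stress, common cause links them | 76.6% and 77.5% in two separate runs |

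The first row is essentially the level of the arm test. The others are essentially its power: the standard error is √(1/90 + 1/45) = 0.183, and Φ(0.5/0.183 − 1.96) = 78%. The association adds almost nothing. The rule cannot tell mediation from direct effects, and it would allow a mechanism of stress reduction to be declared when stress was not reduced.

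Requiring H1(a) as well brings the last row down to 2.4%, at a price. If the app lowers stress only through a behaviour shifted by 0.5 SD, with r = 0.41, the effect on stress is 0.41 × 0.5 = 0.205 SD. Power for that is about Φ(0.205/0.183 − 1.96) = 20%. The stricter rule would miss most truly mediated effects of that size.

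**Step 5: the unnamed arm.** Pooling would change the detectable r from 0.343 (n = 90) to tanh(3.339/√132) = 0.283 (n = 135) and mix the arm difference into the correlation. But sections 1.0 and 20.1 both specify the HMP group, and section 20.4 is the methods text for the hypotheses in 20.1. An analyst has no reason to pool.

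**Step 6: the waitlist correlation as a comparator.** With 45 completers an observed r of 0.3 has a 95% interval of 0.01 to 0.55, against 0.10 to 0.48 in the HMP arm. It could neither establish nor exclude a link specific to the app.

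**The case for a change.** The best case for a change is that it would be cheap and would close a real gap between ambition and analysis. Section 2.3 uses causal language, H2 cannot bear it, no text says H1(b), H1(c) and H2 must agree before a mechanism is claimed, and the waitlist data are already collected. A line of SAP wording would stop a one-arm correlation being oversold.

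Part of this stands. H2 alone cannot show that the app lowers stress through pattern separation or experiential diversity, and any report should say so. It is also true that sections 3.2 and 20.4 omit the arm.

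The rest does not carry. The causal sentence in section 2.3 credits the inclusion of behavioural outcomes in an intervention study, which is what H1(b) and H1(c) deliver; it does not rest on H2. The roaming-entropy sentence expresses an interest, and section 3.3 ranks that outcome as tertiary or exploratory. The feared misreporting is something no section commits to. The joint rule would also lend formal authority to a conclusion it cannot support, since the time order of two changes over the same interval stays unknown and a common cause stays possible. For GPS diversity, collected continuously, the documents define neither a baseline nor a T5 window, so such a rule could not be applied to it as it stands.

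**Conclusion.** No change to the plan. The HMP-only correlation is a sound test of the associational objective it serves, and the randomised comparisons that guard against over-reading it are already planned. The missing arm name in sections 3.2 and 20.4 is clerical, because sections 1.0 and 20.1 supply it. Reading H2 together with H1(a) to (c), and treating any mechanism statement as exploratory, is ordinary interpretation that careful analysts will apply without a rule.

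The limitation is real in size: at r = 0.41 H2 is significant in about 94% of trials under either explanation. The obvious remedy does not remove it, since it is met in about 77% of trials under mediation, under separate direct effects, and with no effect on stress. These figures rest on 90 and 45 completers, two-sided tests, an assumed d = 0.5 for the behaviours, and a change-score simplification of the mixed model. Smaller effects on the behaviour make the joint rule less useful: under mediation at r = 0.41 it is met in 58.4%, 36.8% and 18.5% of trials for d = 0.4, 0.3 and 0.2. The primary endpoint is unaffected.

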20.2 Sample size justification

We plan to enroll 150 participants, assigning two-thirds to the HMP group and one-third to the waitlist control group, and anticipate 10% dropout. This sample size affords us 80% power to detect medium effect sizes (d = 0.5) for our primary outcome of perceived stress at p < 0.05. A recent study of the Healthy Minds Program vs. waitlist control (Hirshberg et al., 2021) identified a similar effect size for a composite "distress" measure, which was an aggregate of perceived stress and PROMIS anxiety/depression scores, and another previous study suggested a SD of 0.5 reflects a minimal clinically important differences for the Perceived Stress Scale (Platinga et al., 2017). For correlation analyses, we have 80% power to detect medium-to-large correlations (r = 0.41) at p < 0.0125 (0.05/4 outcomes).

20.3 Participant population(s) for analysis

Participants will be assigned to HMP and waitlist groups at a 2:1 ratio.

20.4 Statistical methods

Group differences for the intervention will utilize linear mixed effects models with a random intercept and slope for each participant to account for non-independence of error and to maximize use of data with missing observations. We will conduct Pearson correlation analyses using difference scores between baseline and post-intervention/follow-up timepoints to test whether reductions in perceived stress are associated with behavioral or imaging outcomes hypothesized to contribute to differences in perceived stress.

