HMP group participants will be instructed on downloading and installing a study-specific version of the HMP app. The 4-week meditation program will take approximately 60 minutes to complete each week. The program will be self-paced and completed remotely. While completing the HMP each week, participants will listen to podcast-style lessons in the app to learn about meditation from scientists and experts in well-being. The app will also guide participants through seated and active meditations. Participants may have the option to provide demographic and meditation experience information and complete the Healthy Minds Index questionnaire to assess their current level of well-being within the app. The app will collect activity data (e.g., when, how long, and what content was listened to), device type, and GPS data (if enabled by the participant). Participants will also occasionally answer pre- and post-practice questions. The app will not collect any identifying information. Participants will have the option to continue using the HMP app after completing the 4-week program. If they choose to do so, we will continue to monitor their app usage and any other data collected through the HMP app throughout the study to learn more about its long-term impact on well-being. The HMP app is considered an FDA regulated device that should qualify as a "non-significant risk (NSR) device". We are seeking an NSR determination and have, therefore, uploaded an NSR request letter in ARROW (see Drug and Device Documents section, #2 Device Documentation).

Timepoints 2-5 - During & Post-Intervention Activities: HMP group participants will complete online measures (see section **13.2 Schedule of study procedures**) remotely through REDCap for Timepoints 2-5 during the same weeks as the 4-week intervention. The measures will take 10 to 45 minutes to complete each week. Waitlist participants will also complete most of the same measures over 4 weeks. Participants will have approximately one week to complete each set of self-paced activities.

Timepoint 6 - 3-Month Follow-Up: About three months after Timepoint 5, participants will complete a final set of measures (see section **13.2 Schedule of study procedures**) remotely online through REDCap, which will take 30 to 45 minutes.

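### Does section 20.4 leave the primary PSS comparison undefined by giving only the random effects of the mixed model?

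*Combined protocol and SAP*

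**What the plan says.** Section 3.3 sets the primary endpoint: "Scores on the perceived stress scale at post-intervention (T5) controlling for baseline (T1"). Within 3.3, the follow-up visit T6 is attached only to secondary and exploratory endpoints, and the exploratory list ends with "Trajectories of change for self-report outcomes assessed on a weekly basis".

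Section 20.4 gives one method for comparing the groups: "Group differences for the intervention will utilize linear mixed effects models with a random intercept and slope for each participant". The stated purpose is "to account for non-independence of error and to maximize use of data with missing observations". The other method in 20.4, correlation of difference scores, serves the association aim.

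The hypothesis in 20.1 gives no timepoint: "H1: HMP vs. waitlist participants will show (a) lower scores on the perceived stress scale". Section 20.2 states: "This sample size affords us 80% power to detect medium effect sizes (d = 0.5) for our primary outcome of perceived stress". It adds that "another previous study suggested a SD of 0.5 reflects a minimal clinically important differences for the Perceived Stress Scale".

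The schedule in 13.2 collects the PSS at T1, T2-T4, T5 and T6. Section 13.3 places T6 well after the rest: "About three months after Timepoint 5, participants will complete a final set of measures".

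**The concern.** A random slope per participant suggests that time enters as a number. That suits weekly trajectories, which 3.3 ranks as exploratory, better than a single-visit difference adjusted for baseline. Section 20.4 does not say whether visit is a number or a category, whether T1 is a covariate or an outcome row, whether T6 is in the model, or which term is tested. Sections 3.2, 13.1, 20.1 to 20.3 and 20.6 do not supply this either.

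The candidate models do not all estimate the same thing. With five closely spaced visits and one about three months later, a straight line can pull the estimate well away from the T5 difference. Two things would then be at stake. The primary coefficient might be chosen after the data are seen. A true effect of 0.5 SD, the size that 20.2 links to clinical importance, might also be reported as a smaller one.

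**Working it through.** **Inputs from the documents.** 150 participants at 2:1 (100 and 50); 10% dropout (90 and 45); d = 0.5; alpha 0.05 (20.2). PSS at T1 to T6 (13.2); T6 about three months after T5 (13.3).

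**Assumptions not in the documents.** Two-sided test; SD 1; correlation 0.6 between any two visits; T1 to T5 at weeks 0 to 4 and T6 at week 17; effect building linearly from 0 at T1 to -0.5 SD at T5; complete data on 90 and 45. Power is from the noncentral t with 133 df, and SE = sqrt(v x (1/90 + 1/45)), where v is the variance of the quantity tested.

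**1. The plan's own power figure.** A two-group t test at one visit has v = 1.
- 100 vs 50: SE = 0.1732, 0.5/0.1732 = 2.89, power 81.8%.
- 90 vs 45: SE = 0.1826, 0.5/0.1826 = 2.74, power 77.6%.

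The stated 80% lies between these. It fits a comparison at a single timepoint and points to no slope.

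**2. T1-adjusted T5 contrast.** v = 1 - 0.6² = 0.64, SE = 0.1461, 0.5/0.1461 = 3.42, power 92.5%. For correlations of 0.4 to 0.7, power is 84% to 97%. The estimate is -0.50 SD whatever happens at T6.

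For the linear models in steps 3 and 4, T1 is a covariate, weeks are centred at T5, the groups have separate lines, and the group term is tested. With weights w summing to 1, v = 0.4 x sum(w²) + 0.24, where 0.24 = 0.6 - 0.6².

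**3. Straight line through T2-T6.** Weights are 0.2356, 0.2275, 0.2194, 0.2113 and 0.1062, so T5 carries 21%. sum(w²) = 0.2113, v = 0.3245, SE = 0.1040.

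| T6 effect | Estimate (SD) | Power |
|---|---|---|
| persists | -0.33 | 88% |
| half fades | -0.30 | 82% |
| fully fades | -0.27 | 74.5% |

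**4. Straight line through T2-T5.** Weights are -0.2, 0.1, 0.4 and 0.7, so T5 carries 70%.
- Estimate: -0.2(-0.125) + 0.1(-0.25) + 0.4(-0.375) + 0.7(-0.5) = -0.50 SD.
- sum(w²) = 0.70, v = 0.28 + 0.24 = 0.52, SE = 0.1317, 0.5/0.1317 = 3.80, power 96.5%.

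**5. Other effect shapes.**
- Effect already full at T2: the T2-T5 line again gives -0.50 SD and 96.5%. The T2-T6 line gives -0.50 to -0.45 SD and 99-100%.
- Effect appearing only at T5: the T2-T5 line gives -0.35 SD and 75%. The T2-T6 line gives -0.16 to -0.11 SD and 33/24/17%, in the order of the table.

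**6. Group-by-linear-week slope over T1-T6.** Power is 76/12/0% in the same order, with 21% rejection in the wrong direction after full fading. Over T1-T5 the slope has 92.5%.

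**7. Random slope.** The steps above set the random-slope variance to zero. Adding a variance of 0.005 SD² per week² leaves the weights unchanged and raises v at T5 by 16 x 0.005 = 0.08. The powers in step 3 then become about 80/73/65%.

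**The case for a change.** The best case for a change is that the primary coefficient should be named before the data are seen, and that one sentence would do it at no cost. Section 20.6 intends to use every observation collected. That leaves a model including T6 possible, and step 3 shows what a straight line through T6 can do. Step 6 is worse still.

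Part of this stands. The link from endpoint to model term is not written anywhere, and a cautious author would write it.

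The argument about harm is weaker. Step 6 takes a trajectory slope as the primary test, although 3.3 places trajectories among the exploratory endpoints. Step 3 puts T6 on a straight line for an endpoint defined at T5. Using all observations does not require that: with visit as a fixed category, T6 can stay in the model without bending the T5 contrast. Nor is a loss of power the usual result. It depends on an effect shape that the documents do not give, and in step 5 the T2-T6 line has more power than the direct contrast when the effect is full at T2. A model with visit as a category is a sound default, but it does not beat every other model that satisfies 3.3, as step 4 shows.

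**Conclusion.** The gap is one of detail. Section 3.3 says what the primary result is: the group difference in PSS at T5, controlling for T1. Section 20.4 says how dependence between visits and missing observations are handled. One model meets both: visit as a fixed category, T1 adjusted for, a random intercept and slope, and the group contrast read at T5. An analyst following 3.3 would arrive at this or something equivalent. The choice of covariance structure affects the standard error but not what that contrast targets.

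Under the stated assumptions, two readings that respect the T5 endpoint give -0.50 SD with 92.5% to 96.5% power. The shortfall to -0.33 to -0.27 SD arises when a straight line is drawn through T6, which 20.4 does not specify. The power figures depend on the assumed correlation, effect shape, complete data and slope variance, so they show possible consequences and do not demonstrate an error. A clarifying sentence would be harmless, but the plan can be carried out correctly as written, and no change is required.
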